4.1 Main Study Objective

The main objective of our study is to determine if treatment with sirolimus can improve clinical outcomes in hospitalized patients with COVID-19.

4.2 Primary Endpoint:

Progression to respiratory failure requiring advanced support measures, either due to inadequate ventilation (non-invasive or invasive mechanical ventilation) or inadequate oxygenation (CPAP* or high flow supplemental oxygen at rates \geq 15 liters/minute), in patients given sirolimus compared to the placebo group.

4.3 Secondary Endpoints:

Key secondary endpoints:

- Escalation in level of care
- Increase in total lymphocyte count
- Normalization of biomarkers (Ferritin, LDH, and d-dimer)
- Survival to hospital discharge
- Drug safety profile (Incidence and type of adverse and serious adverse events)

Other outcomes measures:

- Fever
- Duration of advanced respiratory support
- Duration of hospital stay (in survivors)
- Time from treatment initiation to death (in non-survivors)
- Need for initiation of other off-label rescue therapies such as Anti IL-6 agents, at the discretion of treating clinicians

* CPAP use for known obstructive sleep apnea will not be considered as disease progression.

5. Study Design

We will employ a randomized, double blind, placebo-controlled study design. 30 patients hospitalized with COVID-19 and meeting the inclusion criteria specified below will be randomized to receive sirolimus or placebo in a 2:1 manner. The treatment regimen and duration are provided in Sections 5.5 and 5.6.

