- Query the patient with regards to any adverse effects from the study medication. This can be done remotely via telephone interview rather than in-person visit in order to minimize study staff exposure as well as preserve PPE

In case a subject is discharged from the hospital before Day 14, every effort will be made to complete the day 14 activities on the day of hospital discharge. In case the duration of hospitalization extends beyond the study duration of 14 days, we will periodically monitor the electronic medical record and record key variables such as the need for advanced respiratory support, duration of hospitalization, duration of ICU status, time spent on mechanical ventilation, and vital status.

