8.5 Other study parameters

Daily chart reviews will be performed to record other variables of interest:

Need for advanced respiratory support: Recorded as Yes/No and type, whether high flow oxygen \geq 15 liters/minute, CPAP, non-invasive, or invasive mechanical ventilation. If a patient receives more than one form of advanced respiratory support in the same day, (e.g. started on non-invasive and worsens to require invasive ventilation, or extubated from invasive to non-invasive ventilation), we will designate the most advanced form of ventilation (in the above scenarios – mechanical ventilation) for that day. The ranking order for the above modes of respiratory support are (from most advanced to least advanced means): 1. Mechanical ventilation, 2. Non-invasive ventilation (e.g. bilevel), 3. CPAP, 4. High flow supplemental oxygen \geq 15 L/minute. Of note, the use of CPAP employed to treat pre-existing obstructive sleep apnea will not count as advanced respiratory support.

Duration of advanced respiratory support: For patients who progress to require advanced respiratory support, the type(s) of support and the time spent on the support (individual modes as well as cumulative, days) will be recorded.

Vital status: The vital status (alive/deceased) will be recorded at study termination as well as at the time of hospital discharge (in case that happens after the 14-day study period). For non-survivors, the time from study initiation to death will also be recorded.

Duration of hospital stay (days): will be recorded starting from the day of admission to the day of hospital discharge. This parameter will only be used for analysis in patients who survive the hospital stay.

9. Risks

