The goal of this pilot study is to determine a meaningful treatment difference in order to conduct a larger confirmatory trial. Given the limited data on treatment responsiveness in COVID-19 populations, we examined various enrollment sizes commensurate with planning a pilot study. Specifically, we undertook a recommended approach for pilot studies in clinical research, which is to not perform hypothesis testing with a significance level set at the traditional value of 0.05.³⁴⁻³⁷ The confidence intervals for the treatment difference were calculated based on demonstrating a reduction in the proportion of subjects needing advanced respiratory support from 0.50 in the placebo group to 0.25 in the sirolimus group. Various levels have been proposed as optimal thresholds for the tolerance of type I error in the context of pilot studies, with the highest being $p=0.25$.³⁴ We chose the type I error rate of 0.2 to denote significant treatment effect between the treatment and placebo arms in our study, as proposed by Stallard.³⁷ A sample size of 30 patients randomized in a 2:1 fashion in favor of sirolimus will allow us to estimate the treatment differences with 80% confidence based on a binomial two-proportion test. A two-sided test will be used since we are unsure if the treatment will have a beneficial effect in this patient population.

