Data Analysis Plan: The primary endpoint of this study is progression to respiratory failure requiring advanced support measures. The difference in proportions of progression between the placebo and sirolimus groups and the 80% confidence interval will be calculated. If the confidence interval for the difference in proportions does not include zero, then we will conclude that the treatment difference is clinically meaningful. Considering the small sample size of our study, the significant impact of age and other pre-existing conditions such as diabetes mellitus on overall prognosis in patients with COVID-19 cannot be accounted for in the primary analysis. Patients will be randomized according to a computer-generated permuted block randomization stratified on age: <50 years, 50 – 64 years, and ≥ 65 years. In case recruitment lags we will add external study sites. In such a scenario, University of Cincinnati and the facilities of the affiliated health systems UC Health, LLC and University of Cincinnati Physicians Company, LLC will follow the same randomization scheme. In case of other external sites, randomization will be stratified based on site in addition to the above-mentioned age-based stratification. As exploratory analysis, we will conduct analyses examining differences based on other prognostic factors and concomitant medications such as corticosteroids, hydroxychloroquine, azithromycin etc. An intent-to-treat analysis will be performed for the primary outcome.

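### Length of stay is compared only in hospital survivors, a group that treatment may itself select, so randomisation does not protect the comparison (minor)

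*Combined protocol and SAP*

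**What the plan says.** Section 8.5 (Other study parameters) says that stay "will be recorded starting from the day of admission to the day of hospital discharge", and then restricts its use: "This parameter will only be used for analysis in patients who survive the hospital stay". Section 4.3 and the synopsis place it in the lowest tier of outcomes and build the restriction into its name ("Duration of hospital stay (in survivors").

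Two neighbouring outcomes matter here. "Survival to hospital discharge" is a key secondary endpoint, so the protocol treats survival as something sirolimus may change. "Time from treatment initiation to death (in non-survivors" is the mirror image of the stay outcome, restricted to those who die.

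Section 15 and the SAP give no method for length of stay: no test, interval, analysis set or treatment of deaths. The analysis-set statement does not reach it: "An intent-to-treat analysis will be performed for the primary outcome".

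Data collection is better than the analysis rule. Section 6.3 provides that "In case the duration of hospitalization extends beyond the study duration of 14 days, we will periodically monitor the electronic medical record", with duration of hospitalisation and vital status among the items recorded. Section 8.5 records vital status at discharge and, for those who die, the time from study start to death.

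**The concern.** Randomisation makes the arms comparable as randomised. It does not make the survivors of each arm comparable once treatment can affect who survives. If sirolimus keeps alive some patients who would have died on placebo, those patients are in the sirolimus average and their counterparts are missing from the placebo average. They are likely to be among the sickest and to stay longest, so the survivor-only difference is pushed towards longer stay on a drug that helped. If sirolimus raises mortality, the push reverses and a harmful drug could look as if it shortens stay. Section 15 says that the direction of effect is uncertain and chooses a two-sided test for that reason, so both cases are in play.

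The stake is interpretive. The trial is a pilot meant to inform a larger one, and a stay result with a misleading sign or size could influence the choice of endpoint there.

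**Working it through.** **Plan's own figure.** There is none for stay or in-hospital mortality, so there is nothing to reproduce. The only design input used is the allocation, "A sample size of 30 patients randomized in a 2:1 fashion in favor of sirolimus", which gives 20 sirolimus and 10 placebo patients.

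**Assumed inputs.** mC and mT are in-hospital mortality on placebo and sirolimus. L0 is the mean stay of patients who would survive on either arm. L1 is the mean stay of rescued patients, who would die on placebo but survive on sirolimus. The drug is first taken to change nobody else's stay. The only fatality figure in the documents is about 2% for COVID-19 overall (Section 3.1), which does not describe hypoxic inpatients; it serves here as the low end.

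**Formula.** Mean stay among placebo survivors is L0. Among sirolimus survivors it is [(1 − mC)·L0 + (mC − mT)·L1] / (1 − mT). The difference is therefore

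D = (mC − mT)(L1 − L0) / (1 − mT).

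| mC vs mT | L0 (days) | L1 (days) | D (days, sirolimus minus placebo) |
|---|---|---|---|
| 2% vs 1% | 10 | 25 | 0.01 × 15 / 0.99 = +0.15 |
| 20% vs 10% | 8 | 15 | 0.10 × 7 / 0.90 = +0.78 |
| 20% vs 10% | 8 | 25 | 0.10 × 17 / 0.90 = +1.89 |
| 30% vs 20% | 8 | 15 | 0.10 × 7 / 0.80 = +0.87 |
| 30% vs 20% | 8 | 25 | 0.10 × 17 / 0.80 = +2.12 |
| equal | any | any | 0 |

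D is also zero if L1 = L0. If the arms are swapped, so that mortality is 10% on placebo and 20% on sirolimus, the same arithmetic gives −0.78 to −1.89 days: the harmful arm looks better.

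**How much true benefit would hide it.** If stay in the other survivors falls by c days on sirolimus, the survivor-only difference reaches zero at c = (mC − mT)(L1 − L0) / (1 − mC). At 20% versus 10%, with L0 = 10 and L1 = 25, c = 0.10 × 15 / 0.80 = 1.9 days.

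**Simulation in which severity drives both death and stay.** There were 400,000 patients per scenario. Stay was 6·exp(1.5s + e) days, with s uniform on 0 to 1 and e normal with SD 0.4; the patients with the highest s die. All of this is assumed.

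- 20% versus 10%, no effect on stay: survivor-only stay is 1.2 days longer on drug. In all patients, hospital-free days to day 28 with death scored zero favour the drug by 0.7, and the proportion discharged alive by day 28 is 77.1% on placebo and 84.6% on drug.
- 30% versus 15%, no effect on stay: survivor-only stay is 1.6 days longer on drug; hospital-free days favour the drug by 1.3; discharged alive by day 28, 68.5% versus 80.9%.
- 20% versus 10%, everyone's stay cut by 5%: survivor-only stay is still 0.5 day longer on drug.
- 20% versus 10%, everyone's stay cut by 10%: survivor-only stay is 0.2 day shorter on drug. With equal 20% mortality, the same cut shows 1.3 days shorter, so most of the benefit is hidden although the sign is right.

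**The case against.** The strongest reply has four parts.

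- **Disclosure and rank.** The outcome is named as survivor-only, sits in the lowest tier, has no test or decision rule, and would be reported beside survival, which ranks above it. As a description of survivors it is correct. This stands as an argument for low priority. It does not make the between-arm comparison valid.
- **Assumed inputs.** Every mortality and stay figure above is assumed, and at low mortality the artefact nearly vanishes. This stands, and is why the range starts at 0.15 day.
- **Noise.** At 20% versus 10%, the artefact comes from about 20 × 0.10 = 2 rescued patients. With 8 and 18 survivors and an assumed SD of 5 to 8 days, the standard error is SD × √(1/8 + 1/18) = 2.1 to 3.4 days, so an artefact of 0.8 to 1.9 days is below one standard error. This stands: it is unlikely to decide a conclusion in this trial.
- **Direction.** A reader might infer that a life-saving drug is bound to look as if it prolongs stay. The documents do not support that. It requires lower mortality, much longer stays in rescued patients, and little shortening of stay in anyone else. The last sits uneasily with the planning assumption that advanced respiratory support falls from 50% to 25%, which could plausibly shorten stay in patients who survive on either arm.

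**Conclusion.** The concern holds as a minor one. The planned stay comparison conditions on a post-randomisation outcome that treatment may change, and nothing in Section 15 or the SAP offsets this. The push is towards apparently longer stay if the drug saves very sick patients, and towards apparently shorter stay if it raises mortality. Under stated assumptions that the documents cannot confirm, the size runs from about 0.15 day (2% versus 1%) to about 0.8 to 1.9 days (20% versus 10%). It is zero with equal mortality, and a modest true shortening of stay can outweigh it.

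It would be wrong to conclude that the observed sign must be reversed or that the trial's main result is compromised. The primary endpoint and its 80% interval rule do not use length of stay.

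**What to change.** In the synopsis, Section 4.3, Section 8.5 and the SAP, define the between-arm comparison of stay in all randomised patients, starting at randomisation rather than admission and using the index admission only. The preferred form is time to discharge alive with in-hospital death as a competing event. An alternative is index-admission hospital-free days to a fixed day (for example day 28), with in-hospital death scored zero and arms compared by ranks. State how patients withdrawn before discharge are handled. Keep survivor-only stay as a labelled descriptive summary. Time to death among non-survivors has the same defect and is best read the same way; the competing-event analysis shows in-hospital deaths by arm anyway.

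A measure of days alive and out of hospital that counts post-discharge events is not recommended. Vital status is specified only at study termination and at discharge (Section 8.5), participation ends at 14 days (Section 7.2), continued record review is optional at consent (Section 6.6), and the follow-up footnote in Section 6.2 names no variables or window. Post-discharge deaths and readmissions would not be captured reliably.

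The cost is wording and a small amount of analysis, because discharge dates, vital status at discharge and time to death are already recorded, including for stays beyond day 14. The downsides are a measure slightly harder to describe than days in hospital, and no capture of events after discharge.

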9.1 Risks of the investigational product

In general, sirolimus is a well-tolerated drug. The most common side effects attributable to sirolimus in clinical trials include stomatitis, diarrhea, abdominal pain, peripheral edema, hypertriglyceridemia, hypercholesterolemia, acneiform rash, headaches and myalgias.^{28,29} Other less common but reported AEs from sirolimus include allergic reactions to the drug including angioedema, proteinuria, increased serum creatinine, impaired wound healing, interstitial pneumonitis, and increased risk of secondary infections and malignancies such as skin cancer and lymphomas.²⁸ Key AEs attributable to sirolimus are summarized in the table below. It is worth mentioning that a large proportion of these AEs are derived from studies in renal transplant patients where patients are taking multiple immunosuppressive medications at the same time, and it is not clear if these AEs can be attributable to the use of sirolimus as a single agent.

Adverse reaction	Approximate Incidence (%)
Gastrointestinal disorders	
Nausea	25 - 35
Vomiting	20 - 25
Diarrhea	25 - 40
Constipation	25 - 35
Dyspepsia	15 - 25
Nervous system disorders	
Headache	20 - 30
Cardiovascular disorders	
Peripheral edema	50
Hypertension	40
Deep venous thrombosis	10
Pericarditis	2
Musculoskeletal disorders	
Myalgias and arthralgias	10 - 15
Skin and subcutaneous tissue disorders	
Skin rash	10 - 20
Acne	20 - 25
Mucositis/stomatitis	40 - 50
Hematologic disorders	
Anemia	20 - 30
Thrombocytopenia	15 - 30
Lipid abnormalities	
Hypertriglyceridemia	40 - 50
Hypercholesterolemia	40 - 50
Pulmonary disorders	
Pneumonitis	1 - 2
Malignant complications	
Lymphoma	1 - 3
Renal disorders	
Increased serum creatinine	30
Proteinuria	5

Infectious complications	
Herpes simplex and other viral infections	8 - 10
Urinary tract infection	20 – 30
Other AEs	
Delayed wound healing	20 - 25

Table: Key adverse reactions associated with the use of sirolimus. This is not an exhaustive list. Percentages for the incidence of a particular adverse event are derived from the FDA label and from a review of multiple clinical trials evaluating adverse effects from sirolimus.^{18,28-32}

The vast majority of the common side effects (e.g. hyperlipidemia, increased risk of malignancies) are of concern with prolonged/long-term use of sirolimus. Since our study duration is limited to 14 days, these measurements may not be of significant concern. Side effects of particular interest given the nature of this study will be incidence of secondary infections and other organ system toxicities (pneumonitis, increased serum creatinine, decreased blood counts). We will carefully monitor for all laboratory abnormalities at baseline and on days 3, 7, and 14. We will also enquire about any possible AEs from the patients at days 1, 3, 7, and 14.

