8.3 Laboratory parameters

The following laboratory parameters will be obtained for our study: CBC (total WBCs, Hb, Platelets), absolute lymphocyte count, AST, ALT, serum creatinine, LDH, ferritin and d-dimer. These labs will be obtained at baseline (within 24 hours of study drug initiation) and at days 3, 7 and 14. In case these labs were drawn in the 24 hours prior to the study stipulated time on

clinical grounds, then we will use those values for the study. If not drawn clinically in the preceding 24 hours, then we will obtain these values as research tests. If COVID-19 biorepository sample obtained on the day of these tests, they can be postponed to the next day. In case a subject is discharged from the hospital prior to the 14-day period or is withdrawn from the study, we will make all efforts to perform the Day 14 assessments on that day.

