14.3.4 Adverse events associated with laboratory testing

The following table highlights the laboratory values that are being obtained as part of the study along with the reference range for normal values. While any value outside the reference range will be classified as abnormal, the clinical significance of those abnormal values will be determined based on the criteria set forth in the table. All lab values identified as clinically significant will be marked as an AE. The causality and attribution of the lab value to the study drug, as well as action items with regards to follow-up and management of laboratory values that are listed as clinically significant, will be adjudicated on an individual basis by the study PI.

Laboratory parameter	Reference Range	Reported as clinically significant if
Serum Creatinine	0.50 – 0.99 mg/dl	≥1.5 times baseline
AST	10 – 35 U/L	≥ 105 U/L (3 times ULN)
ALT	6 – 29 U/L	≥ 87 U/L (3 times ULN)
Hemoglobin	11.7 – 15.5 gm/dl	Decrease of ≥2gm/dL from baseline
Total white blood cells	3.8 – 10.8 x 10 ³ /µL	≤ 3 or ≥ 11.5 x 10 ³ /µL
Absolute neutrophils	1500 – 7800 cells/µL	< 1,000 or > 9,500 cells/µL
Absolute lymphocytes	850 – 3900 cells/µL	< 500 or > 4500 cells/µL
Absolute monocytes	200 – 950 cells/µL	< 150 or > 1,500 cells/µL
Absolute eosinophils	15 – 500 cells/µL	< 5 or > 1,000 cells/µL
Absolute basophils	0 – 200 cells/µL	> 500 cells/µL
Platelet count	140 – 400 x 10 ³ /µL	< 120 or > 450 x 10 ³ /µL

Abbreviations: AST = Aspartate aminotransferase, ALT = Alanine aminotransferase, MCH = Mean corpuscular hemoglobin, MCHC = Mean corpuscular hemoglobin concentration, MCV = Mean corpuscular volume, RDW = Red blood cell distribution width.

While the guidance above is meant to cover all laboratory values obtained during the study, we realize that it may not be able to cover all the unique circumstances that can arise during the conduct of a clinical trial. As such, in rare situations, the study PI may change the clinical significance of a lab value outside of the above guidance. We do not anticipate this situation to arise commonly, however, and if deviating from the above range while assigning clinical significance, the reason for this diversion will be clearly outlined in the subject's study binder. Adverse events related to study medication will be tabulated by body system and by severity using the NCI CTCAE v 5.0.

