Data Analysis Plan: The primary endpoint of this study is progression to respiratory failure requiring advanced support measures. The difference in proportions of progression between the placebo and sirolimus groups and the 80% confidence interval will be calculated. If the confidence interval for the difference in proportions does not include zero, then we will conclude that the treatment difference is clinically meaningful. Considering the small sample size of our study, the significant impact of age and other pre-existing conditions such as diabetes mellitus on overall prognosis in patients with COVID-19 cannot be accounted for in the primary analysis. Patients will be randomized according to a computer-generated permuted block randomization stratified on age: <50 years, 50 – 64 years, and ≥ 65 years. In case recruitment lags we will add external study sites. In such a scenario, University of Cincinnati and the facilities of the affiliated health systems UC Health, LLC and University of Cincinnati Physicians Company, LLC will follow the same randomization scheme. In case of other external sites, randomization will be stratified based on site in addition to the above-mentioned age-based stratification. As exploratory analysis, we will conduct analyses examining differences based on other prognostic factors and concomitant medications such as corticosteroids, hydroxychloroquine, azithromycin etc. An intent-to-treat analysis will be performed for the primary outcome.

16. Identification and access to source data

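### Creatinine and blood-count toxicity is planned only as tabulated cut-off crossings; a descriptive between-arm estimate from the numeric values would add moderate information at almost no cost

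*Combined protocol and SAP*

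**What the plan says.** - **Endpoint.** Section 4.3 lists safety as a key secondary endpoint: "Drug safety profile (Incidence and type of adverse and serious adverse events"). Section 9.1 says that the side effects of particular interest "will be incidence of secondary infections and other organ system toxicities (pneumonitis, increased serum creatinine, decreased blood counts").
- **How a lab value counts.** Section 14.3.4 sets a cut-off for each test, for example creatinine at 1.5 times baseline or a hemoglobin fall of 2 g/dL. Then: "All lab values identified as clinically significant will be marked as an AE". The principal investigator may override a cut-off in rare situations. The only summary planned there is a tabulation, by body system and severity, of events related to study medication.
- **What is collected.** Section 8.3, on creatinine, AST, ALT, the blood count and the biomarkers: "These labs will be obtained at baseline (within 24 hours of study drug initiation) and at days 3, 7 and 14". Section 6.2 shows the same schedule.
- **What is analysed.** Section 15 and the SAP cover the primary endpoint and exploratory analyses by prognostic factor and concomitant medication. They contain no analysis of safety labs as numbers, and no safety level, interval or between-arm estimate.
- **Oversight.** Under Section 14.1 the DSMB reviews unblinded safety data at 7, 15, 22 and 30 subjects.

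**The concern.** Turning a serial measurement into a yes/no event discards how far each value moved, and with 20 and 10 patients there is little information to spare. A moderate average rise in creatinine or fall in hemoglobin may produce only a few crossings. A table of those counts can read as showing no difference even when the recorded values lean one way. Because the planned tabulation covers drug-related events, a crossing judged unrelated may not appear in it at all.

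The pilot is meant to inform a larger confirmatory trial, so a renal or marrow signal that was recorded but never summarised would be missing from that decision.

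**Working it through.** **The plan's own figure.** Section 15 gives "A sample size of 30 patients randomized in a 2:1 fashion in favor of sirolimus", with "We chose the type I error rate of 0.2 to denote significant treatment effect between the treatment and placebo arms in our study", two-sided. At 0.50 versus 0.25, SE = √(0.50×0.50/10 + 0.25×0.75/20) = 0.185. The 80% half-width is 1.2816 × 0.185 = 0.238, so the interval is 0.012 to 0.488 and just excludes zero. With 9 versus 18 patients the half-width is 0.2505, which just includes zero. The stated size is reproduced. It concerns the primary endpoint only; no precision is given for safety.

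**Inputs for the safety check.** From the documents: 20 versus 10 patients, and the creatinine and hemoglobin cut-offs. The 0.20 level is borrowed from the primary endpoint. Assumed, because the documents give no values: normal changes at Days 3, 7 and 14 with correlation 0.6; half the effect at Day 3 and all of it by Day 7; a 15% creatinine rise with SD of log change 0.25 (range 0.20 to 0.35); a 0.5 g/dL hemoglobin fall with SD 1.0 (range 0.8 to 1.3).

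**Crossing at one visit (Day 7).**
- Creatinine: ln 1.5 / 0.25 = 1.62, so 5% of placebo patients cross. On sirolimus, (0.405 − 0.140)/0.25 = 1.06, so 14% cross.
- Hemoglobin: 2/1.0 = 2.0 gives 2%; (2 − 0.5)/1.0 = 1.5 gives 7%.
- Crossing at any of the three visits, by simulation, gives the rates in the table.

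**Counts.** Every 20-versus-10 outcome is enumerated. A difference is called when the 80% Newcombe interval excludes zero. The false-positive rate is evaluated with both arms at the placebo crossing rate.

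**Numbers.** Two-sample t test on Day 7 change, 28 df, noncentrality (shift/SD) × √(20×10/30) = (shift/SD) × 2.582. For creatinine, 0.1398/0.25 = 0.559 and 0.559 × 2.582 = 1.44. For hemoglobin, 0.5 × 2.582 = 1.29. At nominal 0.20 the critical value is 1.31. At the counts' actual error rates it is about 1.5 (creatinine) and 2.0 (hemoglobin).

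| Lab (SD) | Ever cross: placebo / sirolimus | Counts detect | Counts' actual error | Numbers, same error | Numbers, nominal 0.20 |
|---|---|---|---|---|---|
| Creatinine (0.20) | 5.1% / 16.6% | 27% | 4.8% | 41% | 69% |
| Creatinine (0.25) | 11.5% / 25.2% | 34% | 14.1% | 48% | 56% |
| Creatinine (0.35) | 24.5% / 37.6% | 33% | 20.6% | 41% | 41% |
| Hemoglobin (0.8) | 1.6% / 6.0% | 3% | 0.8% | 13% | 62% |
| Hemoglobin (1.0) | 5.4% / 12.8% | 16% | 5.3% | 25% | 50% |
| Hemoglobin (1.3) | 13.5% / 22.8% | 26% | 16.3% | 35% | 39% |

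**Sensitivities.**
- The match above is two-sided. The Newcombe errors are lopsided: in the harm direction they are 5.9% for creatinine and 1.2% for hemoglobin at the middle SDs. Matching on that direction alone gives 44% against about 32% for creatinine, and 15% against 15% for hemoglobin. The hemoglobin gain is therefore fragile.
- With a third of Day 7 values missing (14 versus 7), the numeric figures at nominal 0.20 are 47% and 42%.
- If creatinine doubles in 20% of patients and is unchanged in the rest, the two methods are about equal (41% and 39%).

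**A second route.** Take the 30% creatinine incidence tabulated in Section 9.1 and assume 10% on placebo, which equals a shift of 0.76 SD. At two-sided 0.20, counts detect 31% (Fisher), 49% (Newcombe) or 60% (unpooled interval); numbers detect 74%. These figures are not matched for error. With no true difference, the unpooled interval flags harm in 16% to 22% of trials, against a nominal 10% per side.

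**The case against.** A reader might infer that the plan compares the arms on incidence alone and that a real toxic shift will usually be missed. The documents do not support either statement.

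- **No comparison is specified.** Safety events are tabulated and reviewed by an unblinded DSMB. The 80% rule ("If the confidence interval for the difference in proportions does not include zero") is written for the primary endpoint, so the detection rates above are a yardstick and not a property of the plan. This makes the gap one of omission.
- **The nominal contrasts mislead.** Setting 56% against 34%, or 50% against 16%, compares a t test at a true 20% error rate with an interval that errs 14% or 5% of the time. Most of the apparent hemoglobin gain is a looser error rate.
- **Missing a shift is not peculiar to counts.** It depends on the assumed placebo rate and on the count method: at 5% versus 30%, the Newcombe interval excludes zero in 67% of trials and the unpooled one in 79%. The numeric comparison also misses the modelled shifts about half the time or more at matched error.
- **Mean drift is not the toxicity that Section 14.3.4 defines.** That section concerns individual patients, and when few are harmed the numbers add nothing. Pneumonitis and infections are binary. Platelets and white cells, which have two-directional absolute cut-offs, were not modelled.
- **Day 7 data will be thin.** Early discharge removes values, possibly differently by arm. The 14-versus-7 check addresses precision, not bias.

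All of this stands and limits the size of the point. It does not explain why values collected for toxicities of particular interest have no planned summary.

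**Conclusion.** The point holds as a cheap improvement. Creatinine and blood-count toxicity enters the plan only as tabulated cut-off crossings, and the numeric values behind them are left unanalysed. Under the assumed mean shifts and a two-sided error match, the numeric comparison gains about 14 percentage points for creatinine (48 − 34) and 9 for hemoglobin (25 − 16). It stays ahead across the SD ranges tried. The hemoglobin gain disappears if error is matched in the harm direction alone.

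These sizes rest on shifts, SDs, correlation and time course that are not in the documents. The Section 9.1 incidences come in large part from renal transplant patients on several immunosuppressants, so they are only a rough guide. The evidence supports a descriptive estimate beside the incidence table. It does not support replacing that table or making a formal safety claim.

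**What to change.** Keep the adverse-event incidence table and show it by arm. Add to the SAP's Data Analysis Plan:

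- For creatinine, AST and ALT (log scale), hemoglobin, platelets and white cells, estimate the sirolimus–placebo difference at Day 3 and at Day 7 from a linear model adjusted for the baseline value, with an 80% interval.
- Include dosed patients with a value at that visit, irrespective of attribution or cut-off, and report the number observed per arm.
- Repeat with the last in-hospital value as a sensitivity analysis, because early discharge removes Day 7 values.
- State that these are estimates and not tests, that about one in five 80% intervals will exclude zero by chance, and that no claim rests on them.

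Include the same table in the unblinded DSMB report under Section 14.1.

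The cost is a few lines of SAP text and one table, with no new patients, samples or visits. The downside is multiplicity: six tests at two visits give 12 intervals, so about 12 × 0.2 = 2.4 would exclude zero with no true effect. The descriptive label is therefore essential.
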